2.3.2.2 Initial Treatment Period (Weeks 0-16) and Maintenance Treatment Period (Weeks 16-48)

Eligible study participants will be randomized in a 2:2:2:1 ratio as noted in the Study Schema to:

- Bimekizumab [REDACTED] from Weeks 0 to 48
- Bimekizumab [REDACTED] from Weeks 0 to 48
- Bimekizumab [REDACTED] to Week 16, continuing on [REDACTED] from Weeks 16 to 48
- Placebo to Week 16, continuing on bimekizumab [REDACTED] from Weeks 16 to 48

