10 SAFETY ANALYSES

All analysis of safety variables will be performed using the SS, MS, and AMS.

The AMS will be used for summaries of safety that include data from the Initial Treatment Period and Maintenance Treatment Period.

Summaries of safety will be presented for the Initial Treatment Period, Maintenance Treatment Period, and combined Initial and Maintenance Treatment Period unless specified otherwise.

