10.3 Clinical laboratory evaluations

Laboratory values, including markedly abnormal laboratory values will be presented descriptively by treatment group for the SS, MS, and AMS.

The markedly abnormal tables and those based on common terminology criteria for AEs (CTCAE) grade will be produced only for selected laboratory variables.

For tables where data are summarized by visit, unscheduled and repeat visits will not be summarized, but these data will be included in listings. For tables where multiple measurements over a period of time are considered (as in shift tables), unscheduled and repeat visits will be considered as long as they were collected in the period being summarized (values observed more than 140 days after the last administration of study medication are not considered). All summaries will be presented in SI units and will be based on observed case values. In the case where laboratory values are below the LLQ, then these will be set to the midpoint between 0 and the lower limit of quantification for the purpose of summarizing the data. The following summaries are required:

- A summary of the absolute and change from Baseline values in each laboratory variable by treatment group and visit

- A summary of the number and percentage of participants experiencing markedly abnormal values at any time while on treatment (assessment on or following the first dose of study treatment through the minimum of period of interest (Week 16) or date of last dose + 140 days) by laboratory variable and treatment group. Two separate tables will show results for the Initial Treatment Period (for the SS) and the Initial and Maintenance Treatment Period (for the AMS).
- A summary of the number and percentage of participants with a given CTCAE grade (0,1,2,3, or 4) based on minimum/maximum post-baseline value by laboratory variable and treatment group. Two separate tables will show results for the Initial Treatment Period (for the SS) and the Initial and Maintenance Treatment Period (for the AMS).
- A shift table of the number and percentage of participants experiencing CTCAE grade 0,1,2,3, or 4 values (as applicable) at Baseline to maximum post-Baseline CTCAE grade, by laboratory variable and treatment group. Two separate tables will show results for the Initial Treatment Period (for the SS) and the Initial and Maintenance Treatment Period (for the AMS).

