- A by-participant listing of all laboratory data (including urinalysis) will be provided. This listing will be presented by treatment group and will include: center, participant identifier, age, sex, race, weight, visit, laboratory variable, result (with abnormal values flagged as “L” or “H” accordingly) and unit.

Markedly abnormal values are defined as those with a severity of Grade 3 and above based on the CTCAE criteria Version 4.03. Definitions of markedly abnormal values using the Grade 3 cut points are given in the tables below for age ranges of ≥ 17 years [Table 10–4](#) for markedly abnormal liver function test values, [Table 10–5](#) for markedly abnormal biochemistry values and [Table 10–6](#) for markedly abnormal hematology values). Tables summarizing markedly abnormal values will include a summary (counts and percentages) of markedly abnormal labs observed at any time while on treatment (ie, treatment-emergent markedly abnormal [TEMA]). For this summary, Baseline values and values observed more than 140 days after the last administration of study medication are not considered. The laboratory results classified as Grade 3 or Grade 4 will be summarized and listed separately.

Table 10–4: Definitions of Markedly Abnormal Liver Function Values

Parameter name	Conventional		Standard		Abnormal Designation
	Unit	Criteria	Unit	Criteria	
ALP	U/L	>5.0 x ULN	U/L	>5.0 x ULN	AH
ALT	U/L	>5.0 x ULN	U/L	>5.0 x ULN	AH
AST	U/L	>5.0 x ULN	U/L	>5.0 x ULN	AH
Total Bilirubin	mg/dL	>3.0 x ULN	umol/L	>3.0 x ULN	AH
GGT	U/L	>5.0 x ULN	U/L	>5.0 x ULN	AH

Table 10–5: Definitions of Markedly Abnormal Biochemistry Values

Parameter name	Conventional		Standard		Abnormal Designation
	Unit	Criteria	Unit	Criteria	
Creatinine ¹	mg/dL	> 3.0 x Baseline or >3.0 x ULN	umol/L	> 3.0 x Baseline or >3.0 x ULN	AH
Glucose	mg/dL	<40 >250	mmol/L	<1.7 >13.9	AL AH
Calcium	mg/dL	>12.5 <7.0	mmol/L	>3.1 <1.75	AH AL
Magnesium	mg/dL	>3.0 <0.9	mmol/L	>1.23 <0.4	AH AL
Potassium	mmol/L	>6.0 <3.0	mmol/L	>6.0 <3.0	AH AL
Sodium	mmol/L	>155 <130	mmol/L	>155 <130	AH AL
Cholesterol	mg/dL	>400	mmol/L	>10.34	AH

¹ The markedly abnormal definitions for creatinine are based on the logical or, if either criterion is met the creatinine value will be designated as abnormal high.

Table 10–6: Definitions of Markedly Abnormal Hematology Values

Parameter name	Conventional		Standard		Abnormal Designation
	Unit	Criteria	Unit	Criteria	
Hemoglobin	g/dL	<8.0 >4.0 above ULN	g/L	<80 >40 above ULN	AL AH

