Lymphocytes Absolute	10 ⁹ /L	<0.5 >20.0	10 ⁹ /L	<0.5 >20.0	AL AH
Neutrophils Absolute	10 ⁹ /L	<1.0	10 ⁹ /L	<1.0	AL
Platelets	10 ⁹ /L	<50	10 ⁹ /L	<50	AL
WBC/Leukocytes	10 ⁹ /L	<2.0 >100	10 ⁹ /L	<2.0 >100	AL AH

Abbreviations: AH=abnormal high; AL=abnormal low; ALP = alkaline phosphatase; ALT= alanine aminotransferase; AST = aspartate aminotransferase; dL = deciliter; GGT: gamma-glutamyltransferase; L = liter; mg = milligram; mmol = millimoles; µg = microgram; ULN = upper limit of normal, WBC=white blood cells.

The table for markedly abnormal liver function tests (LFTs) will contain data beyond the CTCAE Grade 3 thresholds outlined in [Table 10-1](#) above in order to allow for a more thorough review of elevated LFTs. There will be 1 table, which will list the count and percentage of participants meeting the below criteria at any time during the study:

- AST: >3xULN, >5xULN, >8xULN, >10xULN, >20xULN
- ALT: >3xULN, >5xULN, >8xULN, >10xULN, >20xULN
- AST or ALT: >3xULN, >5xULN, >8xULN, >10xULN, >20xULN
- Total Bilirubin: >1.5xULN, >2xULN
- ALP: >1.5xULN

For any participant with at least one markedly abnormal LFT (AST >3xULN, ALT >3xULN, bilirubin >3xULN, or ALP >1.5xULN) the New Ratio (nR) will be calculated as the ratio of either ALT or AST (whichever is higher) to ALP, all expressed as multiples of their ULN as follows:

- $nR = [\text{maximum}(\text{AST}/\text{ULN or ALT}/\text{ULN})]/(\text{ALP}/\text{ULN})$

Any pDILI will be summarized (all criteria must be met at the same assessment):

- (AST or ALT > 3xULN) and Total Bilirubin > 1.5xULN
- (AST or ALT > 3xULN) and Total Bilirubin > 2xULN

In addition, a table will be produced to summarize potential Hy's Law cases. The following definition will be used in that table:

- $[\text{AST} \geq 3\text{xULN or ALT} \geq 3\text{xULN}] \text{ and Total Bilirubin} \geq 2\text{xULN}$ in the absence of ALP $\geq 2\text{xULN}$

In order to meet the above potential Hy's Law criteria, a participant must experience the elevation in bilirubin and ALT or AST (and the absence of ALP elevation, if applicable) at the same assessment. For example, a participant who experiences a ≥ 2 x ULN elevation of bilirubin at one visit and a ≥ 3 xULN elevation in ALT (or AST) at a subsequent visit has not fulfilled the Hy's Law criteria.

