10.4 Vital signs, physical findings, and other observations related to safety

10.4.1 Vital signs

The following vital signs variables will be summarized: systolic blood pressure (mmHg), diastolic blood pressure (mmHg), body temperature (°C) and heart rate (beats/min). The following summaries will be provided for the SS:

- A summary of the absolute and change from Baseline value for each vital sign variable by treatment group and visit.
- A summary of the number and percentage of participants experiencing at least 1 markedly abnormal value for a vital sign variable as defined in Table 10–7, by treatment group and period (Initial Treatment Period [SS], and Initial and Maintenance Treatment Period [AMS]). Unscheduled and repeat visits will be considered as long as they were collected in the period being summarized (values observed more than 140 days after the last administration of study medication are not considered).

Table 10–7: Definitions of Markedly Abnormal Blood Pressure Values

Parameter (unit)	Markedly Abnormal Low	Markedly Abnormal High
Systolic blood pressure (mmHg)	<90 and a decrease from Baseline of ≥ 20	>180 and an increase from Baseline of ≥ 20
Diastolic blood pressure (mmHg)	<50 and a decrease from Baseline of ≥ 15	>105 and an increase from Baseline of ≥ 15

A by-participant listing of all vital signs data will be provided. This listing will be presented by treatment group and will include: center, participant identifier, age, sex, race, weight, visit, vital sign variable and result (with abnormal values flagged as “L” or “H” accordingly).

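### Section 10.3 gives the liver-test threshold table a single whole-study window, out of line with its own two-period rule; read literally, isolated elevations below Grade 3 get no count by arm over the 16 placebo-controlled weeks

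*SAP*

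**What the plan says.** Section 10.3 first sets a rule for counts of markedly abnormal values by laboratory variable and treatment group. "Two separate tables will show results for the Initial Treatment Period (for the SS" begins the sentence, which then names the combined Initial and Maintenance Treatment Period for the AMS. The window starts at first dose and runs "through the minimum of period of interest (Week 16) or date of last dose + 140 days". For the treatment-emergent summary, "Baseline values and values observed more than 140 days after the last administration of study medication are not considered".

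Markedly abnormal is defined there as CTCAE Grade 3 and above. Table 10-4 gives the liver cut-offs: ALP, ALT, AST and GGT above 5xULN, total bilirubin above 3xULN.

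Later in the same section comes the liver output: "The table for markedly abnormal liver function tests (LFTs) will contain data beyond the CTCAE Grade 3 thresholds outlined in" a table cited as Table 10-1. Then: "There will be 1 table, which will list the count and percentage of participants meeting the below criteria at any time during the study". The list that follows has AST, ALT, and AST or ALT at 3, 5, 8, 10 and 20xULN, total bilirubin at 1.5 and 2xULN, and ALP at 1.5xULN.

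Section 10 sets a default: "Summaries of safety will be presented for the Initial Treatment Period, Maintenance Treatment Period, and combined Initial and Maintenance Treatment Period unless specified otherwise". Section 2.3.2.2 describes the fourth arm: "Placebo to Week 16, continuing on bimekizumab" for Weeks 16 to 48.

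**The concern.** The liver paragraph presents its output as the markedly abnormal table for liver tests, yet gives it a different number of tables and a different window from the rule set earlier in the section. It restates neither the exclusion of Baseline values nor the 140-day limit, and it names no analysis set.

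Hepatic events are a named safety topic, and the lower cut-offs were added for closer scrutiny of raised liver tests. Only Weeks 0 to 16 are placebo-controlled. If the added cut-offs are counted over the whole study only, the column for participants randomized to placebo is mostly bimekizumab time. Two programmers, one following the general rule and one following the liver paragraph, would deliver different tables.

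**Working it through.** **Step 1. The two instructions side by side (both in the current text of Section 10.3).**

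| | General rule for markedly abnormal values | Liver threshold table |
|---|---|---|
| Number of tables | 2, by period | 1 |
| Window | First dose to the period end or last dose + 140 days, whichever is earlier | Any time in the study |
| Analysis set | SS; AMS | Not stated |
| Cut-offs | Grade 3 and above (Table 10-4) | Down to AST/ALT 3x, bilirubin 1.5x, ALP 1.5xULN |

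The parallel vital-signs summary in Section 10.4.1 keeps the two-period form: "by treatment group and period (Initial Treatment Period [SS], and Initial and Maintenance Treatment Period [AMS".

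**Step 2. Does another planned output count isolated elevations below Grade 3 by arm to Week 16?**

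- The general two-period table uses Grade 3 cut-offs. It counts AST/ALT above 5xULN by period, but not above 3xULN.
- The by-period CTCAE grade and shift tables are limited to selected variables, and Appendix B has no grade rows for ALT, AST, ALP, GGT or bilirubin.
- The pDILI and potential Hy's Law summaries require transaminase and bilirubin criteria at the same assessment. They state no period, so the Section 10 default covers them.
- By-visit values, listings and hepatic TEAE tables do not give threshold counts.

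No stated output clearly does it.

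**Step 3. What the whole-study count holds for the placebo-randomized arm.** Inputs: N = 70 (Section 2.4), and 16 and 32 weeks (Section 2.3.1). Assumptions: full completion, 52.18 weeks per year.

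- On placebo: 70 x 16/52.18 = 21.5 participant-years
- On bimekizumab: 70 x 32/52.18 = 42.9 participant-years
- Share on bimekizumab: 32/48 = 67%

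**Step 4. Effect on a comparison of column percentages.** Assume rare events at constant rates, with bimekizumab-to-placebo rate ratio r and 16-week placebo risk x. A bimekizumab column has 48-week risk 3rx; the placebo-then-bimekizumab column has x + 2rx.

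- Share of the switch-arm cases arising on bimekizumab: 2r/(1 + 2r), which is 67% at r = 1, 80% at r = 2 and 91% at r = 5.
- Ratio of column percentages: 3r/(1 + 2r), which is 1.20 at r = 2, 1.36 at r = 5 and never above 1.5. Over 16 weeks the ratio would be r.
- Difference of column percentages: 3rx - (x + 2rx) = (r - 1)x, the same as the 16-week difference.

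So the ratio is compressed and the absolute difference is not.

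**Step 5. How many cases a 16-week table would show.** The SAP gives no event rates. At assumed placebo rates of 1 to 3 per 100 participant-years, 21.5 participant-years yields 0.2 to 0.6 expected placebo cases, and the chance of none is exp(-0.21) = 81% to exp(-0.64) = 53%.

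**The case against.** The strongest reply is that the two rules need not collide. Markedly abnormal is defined as Grade 3 and above, so the two-table rule never promised the lower cut-offs by period; where the rules overlap, at Grade 3 and above, the by-period count stands. In addition, Section 10.3 opens by saying that laboratory values are presented by treatment group for the SS, MS and AMS. With the Section 10 default, the single table may mean one layout repeated by analysis set, and the table shells, which are not at hand, may settle it.

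Much of this stands. Grade 3 and higher values do get a 16-week count, and the repeated layout is a plausible intention. It does not explain the explicit whole-study window, however, and the Section 10 default yields to any specification to the contrary. The liver paragraph also calls its own output the markedly abnormal table, and the New Ratio rule in the same section uses that label for AST or ALT above 3xULN and ALP above 1.5xULN. The lower cut-offs are therefore not cleanly outside the general rule.

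Two further points stand in full. Laboratory data are summarized by counts and percentages, and no risk difference or interval is planned for them, so no claim about precision is made here. A combined-period AMS table would also mix placebo and bimekizumab time in the switch arm.

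**Conclusion.** The wording is inconsistent and should be corrected, but the point is modest. Read literally, isolated AST/ALT above 3xULN, bilirubin above 1.5x or 2xULN and ALP above 1.5xULN have no count by arm over the placebo-controlled 16 weeks. The switch arm's whole-study count rests on 16 placebo and 32 bimekizumab weeks. The 67% share assumes full completion, and the ratio figures assume rare events and constant rates.

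A reader might infer that the plan has no placebo-controlled look at liver safety, or that the Hy's Law assessment is compromised. The SAP does not support either: Grade 3 and higher values by period, pDILI, potential Hy's Law and hepatic TEAEs all remain. Nor does it support the view that Section 10.3 flatly contradicts itself on every reading, or that a signal would be concealed. One repeated layout is possible, values are listed by participant, and few placebo cases are likely in 16 weeks at the assumed rates. No inferential result depends on this table.

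**What to change.** In Section 10.3, replace the single whole-study table with the same liver criteria by treatment group in two tables: Initial Treatment Period (SS), and Initial and Maintenance Treatment Period (AMS). Apply to both the treatment-emergent window already defined in that section, including the exclusion of Baseline values and of values beyond 140 days after last dose.

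State that the SS table is the placebo comparison. The AMS table still combines placebo and bimekizumab time in the switch arm, and the AMS requires at least one bimekizumab dose (Section 3.5.5). If one layout repeated by period was always intended, saying so and dropping the whole-study phrase is enough.

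In the same paragraph, change the reference from Table 10-1, which lists cardiovascular event classifications, to Table 10-4.

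The cost is a wording change and one more run of the same table on data already collected. The only downside is an additional descriptive output.

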2.2.3.2 Other safety endpoints

The other safety endpoints are

- Adverse events of special interest (Hy's Law)
- Other safety topics of interest: infections (serious, opportunistic, fungal, and TB), neutropenia, hypersensitivity (including anaphylaxis), suicidal ideation and behavior, major adverse cardiovascular events, hepatic events and potential drug-induced liver injury (PDILI), malignancies, and inflammatory bowel disease.

- Absolute change from Baseline in the Patient Health Questionnaire (PHQ-9) score
- Absolute change from Baseline in vital signs
- Absolute change from Baseline in clinical laboratory values (chemistry and hematology)
- Electrocardiogram (ECG) results

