10.2.3.8 Hepatic events and PDILI

- **Incidence of hepatic events TEAEs per 100 subject years by SOC, HLT and PT**

A table for hepatic events will be created based on the SMQ of “Drug related hepatic disorders - comprehensive search (SMQ)”. However, these 2 sub-SMQs are to be excluded: “Liver neoplasms, benign (incl cysts and polyps) (SMQ)” and “Liver neoplasms, malignant and unspecified (SMQ)”. For each of the above SMQs, include all TEAEs which code to a PT included in the Scope=Broad and/or Scope=Narrow.

Note that all AEs meeting the above criteria are to be included. It will not be limited to events that the investigator determined to be related to study drug.

Cases of potential Hy’s Law will be reported separately in a liver function test table.

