Potential hepatotoxicity (meeting one of the PDILI or Hy's Law laboratory criteria at least once) will be considered with and without symptoms potentially associated with hepatitis or hypersensitivity according to the investigator (reported on the Symptoms of Hepatitis and Hypersensitivity CRF page).

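### The potential Hy's Law and pDILI tables count only elevations that coincide at one draw; a participant who crosses both thresholds at different draws is in no combined count

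*SAP*

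**What the plan says.** Section 10.3 plans a table of potential Hy's Law cases. The criteria are AST or ALT at or above 3xULN, total bilirubin at or above 2xULN, and no ALP at or above 2xULN. On timing it says that "a participant must experience the elevation in bilirubin and ALT or AST (and the absence of ALP elevation, if applicable) at the same assessment". It then works an example: bilirubin of 2xULN or more at one visit and ALT or AST of 3xULN or more "at a subsequent visit has not fulfilled the" Hy's Law criteria.

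The pDILI summary in the same section has two tiers, both with AST or ALT above 3xULN: bilirubin above 1.5xULN, and bilirubin above 2xULN. Neither has an ALP condition. The timing rule is the same: "Any pDILI will be summarized (all criteria must be met at the same assessment").

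Four other outputs bear on the point:

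- Section 10.3 has a liver function table "which will list the count and percentage of participants meeting the below criteria at any time during the study". Its rows are AST, ALT, AST or ALT, total bilirubin and ALP.
- Section 10.3 also considers potential hepatotoxicity with and without symptoms, for participants meeting one of the pDILI or Hy's Law "laboratory criteria at least once".
- Section 10.2.3.8 plans a hepatic adverse event table and states that potential Hy's Law cases "will be reported separately in a liver function test table".
- Section 10.3 plans a by-participant listing of all laboratory data.

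Section 2.2.3.2 names Hy's Law as the only adverse event of special interest.

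**The concern.** A table of potential cases serves as a screen: it should pick out participants for medical review, and a missed candidate usually costs more than an extra one reviewed. Transaminases and bilirubin need not be raised in the same sample. If ALT has fallen below 3xULN by the time bilirubin reaches 2xULN, or bilirubin rises first and has fallen by the time ALT crosses its limit, the participant fails the rule.

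The pDILI tiers relax the bilirubin limit and drop the ALP condition but not the timing, so they fill the gap only in part. Elsewhere the SAP often pairs a specific definition with a broader one: malignant with malignant-or-unspecified tumours (Section 10.2.3.2), MACE with extended MACE (10.2.3.3), and definite and probable with possible IBD (10.2.3.6). The Hy's Law and pDILI counts have no counterpart with looser timing.

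At stake is whether a reader of the tables can tell that no participant met both criteria from a result in which some did, at different draws.

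**Working it through.** No sample size, power or alpha figure depends on this rule, so there is no plan figure to reproduce. The check applies the stated rules to hypothetical participants and then asks which planned outputs would show them.

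**Step 1: the rules applied.** Values are multiples of ULN, and ALP is assumed normal throughout.

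| Participant | Visit 1 | Visit 2 | Hy's Law, as planned | pDILI, as planned | Hy's Law thresholds met at any time |
|---|---|---|---|---|---|
| A | ALT 6, bilirubin 1.2 | ALT 2.5, bilirubin 2.5 | 0 | 0 | 1 |
| B | ALT 1.5, bilirubin 2.2 | ALT 4, bilirubin 1.4 | 0 | 0 | 1 |
| C | ALT 6, bilirubin 1.5 | ALT 4, bilirubin 2.6 | 1 | 1 | 1 |

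A and B are not counted because no single visit has both values over their limits. B follows the SAP's own example. C is counted although ALT peaks at visit 1 and bilirubin at visit 2, because both limits are exceeded together at visit 2. What decides is whether the thresholds are ever met together, not where the peaks fall. Had A's bilirubin at visit 1 been above 1.5, the lower pDILI tier would have counted A at that visit.

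**Step 2: the other outputs.**

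- *Any-time liver table.* A appears in the row for ALT above 3xULN and in the row for bilirubin above 2xULN, but nothing shows that it is the same person. Let T be the number with AST or ALT above 3xULN, B the number with bilirubin above 2xULN, and N the number with both at any time. The table gives T and B, so the reader knows only that N ≤ min(T, B).
- *Symptom summary.* It reuses the pDILI and Hy's Law criteria and so inherits the timing rule.
- *Hepatic adverse event table.* It counts reported terms, not laboratory combinations.
- *Laboratory listing.* A can be found there, by reading across visits and comparing each value with its ULN.

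None of these counts the combination across draws.

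**Step 3: size, by illustration only.** Section 2.4 plans 3 × 140 = 420 participants on bimekizumab in the Initial Treatment Period. Assume that exactly one of them resembles A or B. The exact one-sided 95% Poisson upper limits are:

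- planned table: 0 of 420, upper limit 3.00/420 = 0.71%;
- with the any-time row: 1 of 420 = 0.24%, upper limit 4.74/420 = 1.13%.

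The single case is an assumption, and the SAP plans no such interval for this table. For the combined period the denominator would be larger, because the Active Medication Set also includes placebo participants once they receive bimekizumab.

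**The case against.** The strongest reply is that the rule is a deliberate choice, stated without ambiguity, illustrated by an example and applied consistently to pDILI. It contradicts nothing in the SAP, and no passage there says that elevations at different draws must count. All of that stands: this is a request for a supplementary count, not the correction of an error.

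It also stands that existing coverage is more than nothing. The lower pDILI tier catches some staggered episodes. A participant strictly above both limits at different visits appears in two rows of the any-time table, so those rows would not both be zero. Where period-based tables use unscheduled and repeat visits, follow-up draws add chances for the thresholds to coincide.

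A reader might go further and infer that any liver episode whose peaks fall at successive visits is missed. Participant C shows that this is not so. A reader might also infer that cases are lost or that a signal would be turned into zero. The SAP does not support that either: the elevations remain in the any-time table and the listing, no event rate is given, and the SAP does not say how cases are detected during the trial, which may lie in the protocol.

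What the reply does not remove is that no planned table links a participant's transaminase and bilirubin elevations across draws.

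**Conclusion.** The point holds as a gap in reporting. Participants who meet the ALT/AST and bilirubin thresholds, but never at the same draw, are counted in neither the potential Hy's Law table nor the pDILI rows at those thresholds. If they also never meet the lower pDILI tier at one draw, they are in no combined count at all. Their separate elevations stay visible elsewhere.

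The number affected cannot be derived from the SAP; it may be none. The contrast of 0 with 1 in 420 shows only what one reclassified participant would do to the table. The case for acting rests on two judgments: that a table of potential cases should favour sensitivity, and that the only listed adverse event of special interest merits it. No efficacy result, alpha or sample size is touched.

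**What to change.** Keep the same-assessment rows exactly as planned. Add to both the Hy's Law and the pDILI tables a supplementary row, labelled as not requiring the same draw. It counts participants who met the ALT/AST and the bilirubin threshold at any time on treatment, in either order. Alternatively, use a pre-specified window, set from the laboratory visit schedule so that it can link successive draws. For the Hy's Law row, read the ALP condition at the ALT/AST draw. Add a plot of each participant's peak ALT or AST against peak bilirubin, both as multiples of ULN, by treatment group.

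The cost is one extra row in each of the two tables and one figure, from laboratory data already collected. The downside is that a few unrelated elevations will be picked up and will need medical review; the planned rows beside them keep the stricter count visible.
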